## 11.6 Interpretation and Conclusion

The study objective is to provide evidence to show if significant change of PACT-Q2 scores in patients treated with Pradaxa® or VKA. The hypothesis testing for the primary endpoint will be two-sided and significant level will be 0.05. Once the significant is found (p-value < 0.05), the study shows the significant change of PACT-Q2 scores in patients treated with Pradaxa® or VKA.

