- Collection of concomitant diseases/comorbidities,⁸ risk factors,^{9,10} and medical history related to NVAF prior to enrolment, including diabetes mellitus, hypertension, ischaemic heart disease, congestive heart failure, left ventricular dysfunction, stroke, transient ischaemic attack, thromboembolism, vascular disease (myocardial infarction, peripheral artery disease, and complex aortic plaque), abnormal renal function,

abnormal liver function (e.g. cirrhosis), bleeding (e.g. prior major bleeding, predisposition to bleeding/anemia), and alcohol usage. These data will be used to calculate CHA₂DS₂-VASC score and HAS-BLED score[#].

- Collection of current concomitant therapies within 1 month prior to enrolment. Detail information (e.g. indication, start/stop date or ongoing, dosage, route, unit, and frequency etc.) will be recorded if available.
 - For the concomitant therapy as an element for CHA₂DS₂-VASC score or HAS-BLED score calculation^{9,10} including chronic dialysis or renal transplant due to abnormal renal function and medication usage predisposing to bleeding (antiplatelet agents or nonsteroidal anti-inflammatory drugs (NSAIDs)), information prior to enrolment will only be collected as **active/past or never occurred**.
- Collection of serum creatinine, if available, to calculate creatinine clearance (CrCl). The most updated data of serum creatinine assessed prior to enrolment will be collected. CrCl will be calculated according to Cockcroft-Gault formula (using weight collected at the baseline visit and the most updated serum creatinine assessed prior to enrolment).
- Collect the most updated data of lab assessment assessed prior to enrolment for CHA₂DS₂-VASC score and HAS-BLED score calculation^{9,10}. The lab assessments include renal function test (CrCl, as described above), liver function tests (bilirubin, aspartate aminotransferase (AST), alanine aminotransferase (ALT), and alkaline phosphatase (AP)), and international normalized ratio (INR), including prothrombin time (PT).
- For Cohort A only: Collect duration of previous treatment with VKA.
- For Cohort A only: Collect reasons for switching from VKA to Pradaxa[®].
- Document the dosing of Pradaxa[®].
- Patients will be asked to complete the following patient related questionnaires:
 - PACT-Q1 (Cohort B only)
 - PACT-Q2 (Cohort A only)

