9.3.5 Description and justification of patient questionnaires (PACT-Q[®])

The Perception of Anticoagulant Treatment Questionnaire (PACT-Q) was developed as a means to investigate patients' satisfaction with anticoagulant treatment and treatment

convenience in patients with deep venous thrombosis (DVT), pulmonary embolism (PE), or atrial fibrillation (AF).^{13,14} The PACT-Q is a self-administered questionnaire. It can be completed in about 10 minutes. No specific training is required to complete this document.

The original PACT-Q consists of 2 parts and contains 27 items:

1. The PACT-Q1 is composed of a single dimension (7 items), covering the expectations of patients regarding their anticoagulant treatment, and is to be administered before treatment initiation. Only patients in Cohort B (newly initiator) will receive the PACT-Q1 questionnaire at baseline.
2. The PACT-Q2 is composed of 3 dimensions covering: convenience (11 items), burden of disease and treatment (2 items), and anticoagulant treatment satisfaction (7 items). The PACT-Q2 is to be administered to patients once treatment is ongoing. The patients in Cohort A (switchers) will receive PACT-Q2 at all the 3 visits, while the ones in Cohort B (initiators) will receive the questionnaire at Visit 2 and Visit 3.

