##### Cohort B (patients newly initiated Pradaxa® or VKA)

- Mean difference in the PACT-Q2 scores at the second (30-45 days) and the last assessment (150-210 days) compared between 2 treatment groups. The difference will be calculated as (PACT-Q2 scores of *Pradaxa®* minus PACT-Q2 scores of VKA at Visit 2, PACT-Q2 scores of *Pradaxa®* minus PACT-Q2 scores of VKA at Last Visit).

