## 11 STATISTICAL METHODS

### 11.1 Primary Hypothesis

This study is aim to describe the treatment perception from patients with non-valvular atrial fibrillation (NVAF) receiving Pradaxa® or VKA for stroke prevention by using the self-estimation questionnaire of PACT-Q during a 6-month study period. The hypothesis for the testing is

$$H_0: \text{Change} = 0 \text{ vs. } H_a: \text{Change} \neq 0$$

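### SAP 11.1 and 11.6 state a change hypothesis and a change conclusion covering both drugs, but the planned primary analyses yield a change from baseline only in Cohort A switchers

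*SAP*

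**What the plan says.** SAP 11.1 describes the study population as patients on either drug, and then states a single pair of hypotheses: change equal to zero against change not equal to zero. SAP 11.6 adds the decision rule: "The hypothesis testing for the primary endpoint will be two-sided and significant level will be 0.05". Once that threshold is met, "the study shows the significant change of PACT-Q2 scores in patients treated with Pradaxa® or VKA". The rule names no cohort and no visit.

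The questionnaire schedule differs by cohort. At the baseline visit, Protocol 9.2.3 lists "PACT-Q2 (Cohort A only"), and Protocol 9.3.5 says that "the ones in Cohort B (initiators) will receive the questionnaire at Visit 2 and Visit 3". SAP Table 7.1 has the same schedule.

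The endpoint sections keep the cohorts apart. In SAP 10.2 and 11.3 the Cohort A endpoint is each later visit minus Visit 1. For Cohort B it is "PACT-Q2 scores of *Pradaxa®* minus PACT-Q2 scores of VKA at Visit 2", with the same subtraction at the last visit, in propensity-matched pairs. The only other planned change is last visit minus Visit 2 (SAP 10.3 and 11.4), for Cohort A. SAP 11.3 also promises a summary of change from baseline without saying that it applies to Cohort A alone.

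**The concern.** The hypothesis and the conclusion rule are both written in terms of change, and the conclusion covers patients on either drug. The endpoint definitions give a change for only one of the two cohorts, and nobody in that cohort is being followed on VKA.

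Followed literally, the rule goes wrong in two ways. A significant before-after result in the Cohort A switchers, which has no control group, would satisfy a sentence that also speaks for VKA patients. A significant Pradaxa-minus-VKA difference in Cohort B would be reported as a change over time. This is the prespecified interpretation of the primary endpoint, so the sentence is likely to guide how the study report words its main finding.

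**Working it through.** **Planned numbers** (Protocol 9.5, SAP 7.4)

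- Cohort A, switched to Pradaxa: about 300.
- Cohort B: about 500 Pradaxa initiators and 200 VKA initiators, 500 + 200 = 700.
- Total: 300 + 500 + 200 = 1000, which reproduces the plan's own total.

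The documents give no power calculation, and this point does not depend on one.

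**Step 1: who can have a change from baseline.** It needs a PACT-Q2 score at Visit 1 and at a later visit.

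| Group | PACT-Q2 at Visit 1 | PACT-Q2 at Visits 2 and 3 | Change from baseline possible |
|---|---|---|---|
| Cohort A (Pradaxa after VKA) | yes | yes | up to 300 |
| Cohort B, Pradaxa initiators | no | yes | 0 of 500 |
| Cohort B, VKA initiators | no | yes | 0 of 200 |

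The share of planned patients is 300 / 1000 = 30%. In Cohort B it is 0 / 700, and among VKA initiators 0 / 200.

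**Step 2: which changes are planned.** Visit 2 minus Visit 1 and last visit minus Visit 1 are primary, and last visit minus Visit 2 is secondary. All three are for Cohort A. None is planned for Cohort B.

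**Step 3: set the primary comparisons against 11.1 and 11.6.** There are two cohorts and two visits, so at least 2 × 2 = 4 primary comparisons.

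| Primary comparison | Quantity (SAP 10.2, 11.3) | Hypothesis stated in 11.1? | Does the 11.6 sentence describe it? |
|---|---|---|---|
| Cohort A, Visit 2 | within-patient change | yes | only for Pradaxa switchers |
| Cohort A, last visit | within-patient change | yes | only for Pradaxa switchers |
| Cohort B, Visit 2 | matched difference between groups | no | no, it is not a change |
| Cohort B, last visit | matched difference between groups | no | no, it is not a change |

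In none of the four rows does rejecting the null show a change over time in VKA patients. A Cohort B rejection shows that the matched groups differ at that visit. It does not show that either group moved.

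**The case against.** The strongest reply is that the operative analysis is sound. Protocol 9.3.2.1 and 9.7.1 and SAP 6.2.1, 10.2 and 11.3 all separate the Cohort A change from the Cohort B difference. SAP 11.3 fixes the subtraction, the matching, the test and the alpha. The Cohort B null of zero mean difference is implicit in the paired test. The phrase in 11.6 echoes the population named in Objective 1 and may be no more than loose wording. SAP section 12 says the plan follows the protocol unchanged. Nobody would be in doubt about what to compute.

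Most of this stands, and it limits the severity. It does not rescue 11.6, which is a rule about what may be concluded and not a description of the population. As written, the rule permits a claim that no planned analysis supports.

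Three stronger readings are tempting, and the documents do not support them:

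- *That Cohort B patients can have no change score at all.* Both cohorts complete PACT-Q2 at Visits 2 and 3, so a Visit 3 minus Visit 2 change could be computed for up to 700 Cohort B patients, including 200 on VKA. It is simply not planned. Only change from baseline is unavailable.
- *That the rule is invalid because it carries no direction.* A two-sided rejection at 0.05 properly supports a non-directional statement. The subtraction order is fixed in SAP 10.2 and 11.3, and 95% confidence intervals are to be reported, so the sign will be visible.
- *That 11.6 fails because it names no PACT-Q2 dimension.* Whether and how the dimensions are scored is a separate question of endpoint definition that runs through the whole SAP. It is not a defect particular to this section.

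**Conclusion.** The point holds within limits. The single hypothesis in SAP 11.1 fits Cohort A only, and the conclusion in SAP 11.6 is wrong as written for VKA patients and for Cohort B. The change it refers to is available from baseline in about 300 of 1000 planned patients (30%), all switched to Pradaxa, and in none of the roughly 700 in Cohort B or the roughly 200 VKA initiators.

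A reader might infer that the primary analyses themselves are unsound. The documents do not support that: correctly worded conclusions, one per cohort, can follow from the tests in SAP 11.3. The defect lies in the hypothesis and conclusion text. It should be corrected, but it ranks below a must-fix because no planned test or estimate changes.

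The counts rest on the planned allocation, which the documents call an estimate that will follow real-world practice. The zeros do not depend on it, because they follow from the questionnaire schedule.

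**What to change.** - **SAP 11.1:** state two hypotheses. Cohort A: mean change from baseline is zero, at Visit 2 and at the last visit. Cohort B: mean matched difference, Pradaxa minus VKA, is zero, at Visit 2 and at the last visit.
- **SAP 11.6:** replace the single sentence with conclusions for each cohort and visit, tied to the signed estimate and 95% confidence interval already planned. Describe the Cohort A result as an uncontrolled within-patient change in switchers and the Cohort B result as a difference between matched groups. Say that no change over time is claimed for VKA patients.
- **SAP 11.3:** limit the summary of change from baseline to Cohort A.

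The cost is SAP wording only, in a document still marked as a draft. No data collection, test or sample size is affected. The price is a narrower conclusion than 11.6 now allows.

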## 12 SUMMARY OF CHANGES TO THE PROTOCOL

The initial statistical analysis plan will follow the protocol design and no changes or differences will be planned in the initial statistical analysis plan.

## 13 APPENDIX

### 13.1 Mock-up Tables

All statistical tables will be presented corresponding to the content of mock-up tables.

DRAFT

